ACCORD	Academic and Clinical Central Office for Research & Development - Joint office for The University of Edinburgh and Lothian Health Board
ACL	Anterior Cruciate Ligament
CEAC	Cost-Effectiveness Acceptability Curve
CI	Chief Investigator
CRF	Case Report Form
EQ-5D	EuroQol 5 Dimension Health Survey
ECTU	Edinburgh Clinical Trials Unit
FJS	Forgotten Joint Score
GCP	Good Clinical Practice
HCRU	Health Care Resource Use
HTO	High Tibial Osteotomy
ICER	Incremental Cost-Effectiveness Ratio
ICH	International Conference on Harmonisation
JLA	James Lind Alliance
KOOS	Knee Osteoarthritis Outcome Score
MRAV	Minimum Requirements /Acceptable Variation (proforma)
NICE	National Institute for Health and Care Excellence
NJR	National Joint Registry
OA	Osteoarthritis
OKS	Oxford Knee Score
PKT	Personalised Knee Therapy
PCL	Posterior Cruciate Ligament
PI	Principal Investigator
PROM	Patient Reported Outcome Measure

PSA	Probabilistic Sensitivity Analysis
PSS	Personal Social Services
TKR	Total Knee Replacement
QA	Quality Assurance
QALY	Quality Adjusted Life Year
REC	Research Ethics Committee
SOP	Standard Operating Procedure
UKKOR	United Kingdom Knee Osteotomy Registry

1 INTRODUCTION

1.1 BACKGROUND

Osteoarthritis (OA) of the knee is a degenerative joint disease which causes knee pain and disability. The options for treatment are either non-surgical (counselling, painkillers, physiotherapy, walking aids, steroid injections) or surgical. In patients >60 years with disabling knee OA, surgery with knee replacement (partial or total) where the joint is excised and replaced with an artificial metal/plastic implant, has been proven to be successful. However, in patients <60 years knee replacement is not as successful and is associated with a higher failure rate, poor patient reported outcome scores and an earlier requirement for redo-knee replacement (7,8,9,10,11). Realignment of the lower leg with a procedure called high tibial osteotomy (HTO) has shown promise by relieving pain and improving function in patients with knee OA (1,2). A wedge is opened just below the knee to realign the entire lower leg in a manner so that the weight-bearing axis (hip to ankle) passes through the middle part of the knee away from the diseased and arthritic inner half of the knee (Figure 1). Since the native knee joint is preserved in HTO, it is a desirable surgical option in active patients <60 years with the aim of avoiding knee replacement altogether or delaying the need for knee replacement until they are >60 years, when results become more predictable. Published data suggests that surgical treatment of knee OA with HTO avoids the need for a knee replacement in around 90% of patients for 5 years and 70% of patients for 10 years after the operation (1,2). However, the clinical and cost effectiveness of surgical treatment with HTO has never been compared with non-surgical treatment in patients <60 years with knee OA. This trial is aimed at filling this evidence gap.

[figure not shown]

Figure 1: A. The black line is drawn from the centre of the hip to the centre of the ankle and represents the weight-bearing axis (how the body weight passes through the leg). Normally this weight-bearing axis should pass through near the middle of the knee. In this patient suffering from knee OA the weight-bearing axis is abnormal and passes through the inner diseased half of the knee instead of near the middle of the knee **B:** A wedge has been opened just below the knee joint and stabilised with plates and screws in the operation called high tibial osteotomy (HTO). By opening this wedge of bone, the overall alignment of the lower leg and its weight-bearing axis is altered as shown in **C.** The lower leg has been realigned so that the weight-bearing axis (black line) now passes through the middle of the knee, away from the diseased inner half of the knee following HTO relieves pain and reduces disability with preservation of the native knee joint.

1.2 RATIONALE

1.2.1 Intervention – High tibial osteotomy

A. Rationale: The standardisation of the surgical technique with the so-called ‘medial-opening wedge’ HTO has permitted controlled measured deformity corrections, secure fixation with locked plates and quicker rehabilitation. These advancements addressed previous shortcomings of the technique which has now remained stable for the past 15 years (1,2,12,16,18,19, 20). In 2021, a consensus document was published in the UK regarding indications for surgery, decision making, surgical planning, technique, post-operative assessment and recovery. The consensus statements were formulated by a panel of 29 UK based knee surgeons who regularly undertake osteotomy (61). The following key consensus statements (61) support the rationale for the MOTION trial:

1. Kellgren Lawrence Grade 4 (bone on bone) unicompartment arthritis is not considered to be a contraindication to osteotomy.
2. Bipodal weight-bearing long leg alignment imaging should be performed in all cases prior to osteotomy. The mechanical axis of the femur and tibia should be calculated in each case and the site of osteotomy individualised based on the deformity present. This can be undertaken using standard digital imaging software or dedicated osteotomy planning software
3. Prior to performing osteotomy an MRI scan of the knee is recommended to assess the entire knee and the suitability for osteotomy. It is not essential to perform a concurrent arthroscopy. However, if arthroscopy is performed osteotomy can still proceed when appropriate, in patients with grade IV degeneration within the patellofemoral joint.
4. The planned osteotomy method and correction point is dependent on the indication and the severity of the disease. It should be individualised with the general aim of shifting the mechanical axis out of the diseased compartment.

B. Risks: The surgery is associated with general risks including infection, bleeding, neuro-vascular injury and thromboembolic complications. Procedure related risks include intra-operative fracture, non-union of osteotomy, under/overcorrection and conversion to knee replacement. Overall, major complications and severe adverse

events following the modern HTO are now much lower than previously reported with rates between 5%- 10% in the published literature (1,2,18,19,20).

C. Review of evidence – High tibial osteotomy (HTO): A Cochrane review identified 21 randomised studies examining HTO in 1065 patients (1). The mean number of participants in the 21 studies was 52 (range 30-100) and mean age was 60 years (range 42-67 years). None of these studies compared HTO with non-surgical treatment. 19 studies compared different HTO techniques and 2 compared HTO and partial knee replacement. HTO reduced pain and improved knee function in patients with knee OA. However, this conclusion was based on within-group comparisons, and not on non-operative controls. The two studies comparing HTO and partial knee replacement reported no significant differences between the treatments at 7.5 years in terms of treatment failure (risk ratio=1.32, 95% confidence interval (CI) 0.84-1.87) and pain/functional outcome (precise treatment effect not estimable). However, a probabilistic analysis of systematic review data at 10 years following surgery found that HTO was most likely to be cost-effective in patients <60 years and partial knee replacement in patients >60 years (12). Registry data on 3195 HTOs performed between 1987-2008 in Finland demonstrated that 89% (95% CI 88 to 90) did not need a knee replacement within 5 years and 73% (95% CI 72 to 75) did not need one within 10 years (2). Such longer-term survival and satisfactory patient reported outcomes after HTO have also been reported in a recent systematic review of HTO, but the same review also recognised the lack of high-quality studies investigating HTO (22). Finally, HTO does not compromise the later requirement for knee replacement. Joint registry data from Denmark (20) has shown that, when corrected for age and gender, the 10 year survival of knee replacement is not significantly worse when performed after HTO (n=1044) compared to without prior HTO (n= 63,763): 91% compared to 94% (hazard ratio 1.19, p=0.09).

1.2.2 Comparator – Non-surgical treatment (Personalised Knee Therapy, PKT)

A. Rationale: The MOTION non-surgical intervention is a specialised package of knee rehabilitation and represents physiotherapist-led best-care for medial compartment knee OA. It is based on best-practice guidance and was developed with a team of physiotherapy academics from Edinburgh Napier University and clinical specialist physiotherapists from NHS Lothian following an evidence review and with considerable PPI involvement throughout. Our PPI group reviewed the proposed rehabilitation package and considered it to be very different from the physiotherapy they may have received in the community before referral to secondary care. This package of 'Personalised Knee Therapy' (PKT) has also been 'road-tested' at the lead site by the co-applicant (DH) as part of the development of the MOTION trial drawing on the experience of delivering non-operative interventions in multi-site clinical trials in the UK (32,35). Patients were particularly keen to ensure a comprehensive non-operative intervention that is distinct from any previous therapy they may have received earlier in the disease process (prior to referral to secondary care). A core package will deliver (a) progressive structured exercise programme (b) advice on lifestyle, pain management and (where appropriate) weight management. There will be an optional inclusion of biomechanical interventions (bracing or insoles), manual therapy, steroid injection and treatment of additional co-existing symptoms (that interact with and exacerbate the knee symptoms) where this falls within local usual care. The intervention will be delivered over 6 outpatient contact sessions with a specialist physiotherapist over a period not exceeding 4 months.

B. Risks: The risks with non-surgical intervention are much less compared to the surgical intervention but include pain exacerbation from exercise therapy, steroid induced pain exacerbation or joint infection and skin breakdown from brace/orthotic usage.

C. Review of evidence - Non-surgical treatment: The NICE clinical guideline CG177 emphasises a holistic approach to non-surgical management that includes non-pharmacological treatments, pharmacological treatments and steroid injections (4). A Cochrane review of the effectiveness of exercise alone in knee OA concluded that high-quality evidence indicates that land-based therapeutic exercise provides short-term benefit that is sustained for at least 2-6 months after cessation of formal treatment in terms of reduced knee pain, and moderate-quality evidence showing improvement in physical function among people with knee OA (23). Recent systematic reviews from international patient and public organisations dedicated to improving the treatment of OA have also provided substantial evidence to suggest moderate effectiveness of non-surgical treatment for knee OA (24,25,26). In a randomised trial published this year, patients with knee OA who underwent physiotherapy had less pain and functional disability at 1 year than patients who received an intraarticular glucocorticoid injection (27). A Danish randomised controlled trial (100 patients) compared the efficacy of a 12-week non-surgical treatment program with 'usual care' in patients with knee OA (28). The treatment program consisted of individualized progressive neuromuscular exercise, patient education, insoles, dietary advice and analgesics, while usual care comprised two leaflets with information and advice on knee OA and recommended treatments. Compared with usual care, patients undergoing the treatment program improved more in the Knee injury and Osteoarthritis Outcome Score (KOOS) adjusted mean difference 9.6 (95% CI, 4.4-14.8, MCID 8-10). In a second randomised controlled trial, the same research group found that 66% of patients receiving the intervention chose to delay knee replacement for at least 2 years (29). Around 12,796 patients with knee OA have now taken part in a tailored non-surgical management program of exercise and education in Denmark. This was found to be effective in reducing pain by 13.4 points (95% CI; 9.7 to 17.1) on a 0-100 scale (30). Finally, local data from Edinburgh (lead centre) indicates that initial non-surgical management of symptomatic knee OA in primary care fails to meet minimum treatment guidelines in the vast majority of patients and suggests that a tailored approach may be more successful in delaying the need for knee replacement (31,32).

1.2.3 Why this research is needed now, with reference to current NHS policy/practice

Our proposal is timely because both the number of patients with knee OA and the average life expectancy is expected to increase dramatically over the next decade, and the enormous health and economic burden of surgically treating knee OA has now been recognized by the NHS and worldwide (3,4,33). The uncertainties in relation to the optimal treatment options detailed in this proposal have also been recognised by the James Lind Alliance (JLA) which has designated the surgical and non-surgical options for the treatment of knee OA as a Top 10 Priority Setting Partnership in 2016 (34). The research questions we have formulated for this proposal are directly aligned to JLA surgical priorities 1,4, 5, 6, 7 and 10, JLA non-surgical priorities 1,2,3 and 6 and JLA other important priorities 2 and 3 (www.jla.nihr.ac.uk/priority-setting-partnerships/early-hip-and-knee-osteoarthritis/top-10-priorities.htm). This study has the approval of the British Association for the Surgery of the Knee (BASK; www.baskonline.com).

2 STUDY OBJECTIVES

2.1 OBJECTIVES

The objective of this trial is to conduct a pragmatic, multicentre, randomised controlled trial to determine whether the intervention is superior to comparator by answering the following two research questions:

(1) For patients <60 years with medial compartment knee OA, what is the relative clinical effectiveness (pain relief, improvement in function, quality of life, return to work) of HTO compared with non-surgical management at 24 months?

(2) For patients <60 years with medial compartment knee OA, what is the relative cost-effectiveness of HTO compared to non-surgical management at 24 months and as modelled over a lifetime horizon?

2.2 ENDPOINTS

The primary and secondary endpoints will be captured within the following framework: **Population** - NHS patients <60 years with symptomatic knee OA localised to the medial compartment in whom surgical intervention is indicated. **Intervention** - Surgery with medial opening wedge HTO followed by standard postoperative rehabilitation based on local pathways. **Comparator** - Non-surgical intervention with Personalised Knee Therapy (PKT) delivered within an NHS physiotherapy department.

Primary endpoint

The primary outcome is the composite 24-month Knee Injury and Osteoarthritis Outcome Score (KOOS) score (www.koos.nu).

Secondary endpoints

1. Minimum requirements/acceptable variation (MRAV) proforma completed between 6 -12 months post intervention (note that this interval may be different from the same period post-randomisation due to NHS waiting lists)
2. KOOS composite score 12 months post-randomisation.
3. Five separate KOOS subscales at 12 and 24-months post randomisation.
4. Oxford Knee score (OKS, www.innovation.ox.ac.uk) at 12 and 24- months post-randomisation (46).
5. Forgotten Joint Score-12 (FJS-12, www.forgotten-joint-score.info) at 12 and 24-months post-randomisation (47,48).
6. EuroQol EQ-5D-5L score ([EQ-5D-5L – EQ-5D \(euroqol.org\)](http://EQ-5D-5L - EQ-5D (euroqol.org))) (49)
7. Pittsburgh Sleep Problem Scale at 12 and 24-months post randomisation (32)
8. Return to Work/Employment Questionnaire (9,10).

9. Additional study-knee related operative intervention at 12 and 24-months post randomisation

10. Intraoperative and postoperative complications 12 and 24 months post-randomisation

11. Health Economic Evaluation Outcomes

- a. Health and social care resource utilisation and associated NHS and PSS cost and Quality Adjusted life years (QALY) at 24 months
- b. Incremental Cost per QALY at 24 months
- c. NHS and PSS cost, and QALYs as modelled over a lifetime horizon to account for future impacts on the need for TKR and associated revision surgery and their timing relative to retirement
- d. Incremental Cost per QALY as modelled over a lifetime horizon to account for future impacts on the need for TKR and associated revision surgery and their timing relative to retirement.

3 STUDY DESIGN

MOTION is a multi-centre, prospective randomised open blinded endpoint (PROBE) parallel-group controlled trial. Patients will be randomly assigned to one of the two treatment arms, in a 1:1 ratio, centrally, by the Edinburgh Clinical Trials Unit (ECTU) via a web-based system. To ensure groups are balanced, a minimisation algorithm will incorporate age, sex, body mass index and baseline KOOS score. Patients will be randomised to either the surgical intervention of High Tibial Osteotomy (HTO) or non-surgical intervention of Personalised Knee Therapy (PKT).

Included: Patient <60 years with symptomatic medial compartment knee OA who the treating orthopaedic surgeon considers a suitable candidate for medial opening wedge HTO

Enrollment

Excluded:

- Not meeting inclusion criteria
- Declined to participate
- Due to exclusion criterion

Randomized 1:1 (n=224)

Allocation

Allocated to non-surgical treatment – Personalised Knee Therapy (n=112)

- Detail those who received allocated intervention
- Detail those who did not receive allocated intervention (give reasons)

Intervention delivered within NHS according to local protocols

Allocated to surgical treatment – High Tibial Osteotomy (n=112)

- Detail those who received allocated intervention
- Detail those who did not receive allocated intervention (give reasons)

Intervention delivered within NHS according to local protocols

Follow-Up

Lost to follow-up (give reasons)

Discontinued intervention (give reasons)

Analyses

Analysed

- Excluded from analysis (give reasons)

6-12 months post-intervention: Minimum requirements and acceptable variation

12 months post-randomisation: KOOS, FJS, OKS, EQ5D-3L, Sleep Problem Scale, Return to Work, Additional operative intervention in study knee, Complications, Health Economic Evaluation

24 months post-randomisation: KOOS, FJS, OKS, EQ5D-3L, Sleep Problem Scale, Return to Work, Additional operative intervention in study knee, Complications, Health Economic Evaluation

The setting will be within the orthopaedic surgical departments of NHS hospitals in the UK that treat patients with medial compartment knee OA with facilities to support the trial. Patients will be followed up for 24 months following recruitment. The study design incorporates a 9-month internal pilot which will be reviewed by the Data Monitoring Committee (DMC), Trial Steering Committee (TSC) and the funder to determine whether the study progresses to the full trial. We plan to open at least 5 sites during the pilot phase (see Table 1 below). An embedded process evaluation will record specific factors affecting the recruitment rate to provide further data to optimise recruitment. Following the pilot and meeting the stop / go criteria additional sites will be invited to participate.

Table 1: Stop/Go criterion for Internal pilot phase

Progression Criterion – Internal pilot	Red	Amber	Green
Trial recruitment			
Number of sites opened during pilot	2 or less	3-4	>5
Total number of participants recruited	<10	10-20	>20
Recruitment rate/site/month	<0.2	0.2-0.7	>0.7
Non-adherence			
Cross-over rate (%)	>50%	20-50%	<20%
Off-protocol intervention rate (%)	>30%	10-30%	<10%

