6 STUDY ASSESSMENTS

Participant Follow-up at 12 and 24 months

All available methods of communication will be used for the study assessments including email, post, telephone and NHS approved video links (e.g. NearMe), with a maximum of two reminders sent where required. The preferred method for collection of baseline data will be with a face-face consultation. Where local circumstances prevent this, baseline data may also be collected by telephone or video link. After collection of the baseline data, follow up will occur at two further intervals - 12 and 24 months post-randomisation, with all study assessments at these time points undertaken remotely via email, post or telephone.

Minimum requirements/acceptable variations (MRAV) proforma

A standardised minimum requirements/acceptable variations (MRAV) proforma will be completed for each participant approximately 6 months post intervention to record the fidelity of the trial interventions. This proforma will be completed by the local research team at each participating centre. It should be noted that this proforma is collected from approximately 6 months post-intervention, and this interval may be different from the time period since randomisation due to NHS waiting lists. In the Personalises Knee Therapy (PKT) group, data will be collected and recorded at each one-to-one session. The date of the last one-to-one physiotherapy session (usually the 6th session) will be considered as the date for completion of the intervention.

Table 2: Tabulated summary of assessments						
ASSESSMENT	Screening	Baseline	6-month MRAV proforma (HTO)	6-month MRAV proforma (PKT)	12-month PROMS	24-month PROMS
Who is responsible for assessment?	Local site team	Local site team	Local site team	Local site team	ECTU	ECTU
Allowed variation in months			±6	±6	±3	±3
How is assessment done?	Clinic review and/or Medical records review	Clinic review	Medical records review	Patient attendance at 6 supervised physiotherapy sessions Medical records review Patient exercise diary review	Email and/or Post and /or Online portal	Email and/or Post and /or Online portal
Assessment of eligibility criterion	X	X				
Log of eligible patients excluded (declined, exclusion criterion, other reason)		X				
Written Informed consent		X				
Baseline data & demographics		X				
Randomisation		X				
Minimum requirement/acceptable variation (MRAV) proforma			X	X		
Primary outcome score – KOOS		X			X	X

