9 STATISTICS, DATA ANALYSIS AND PROCESS EVALUATION

9.1 Sample size calculation

The minimally clinically important difference (MCID) for the primary outcome measure is 8-10 (see KOOS website www.koos.nu), so we have used a value of 9, the mid-point of this range. To account for 20% unidirectional crossover from the non-surgical arm to the surgical arm, we have used an MCID of 7.2. If the observed treatment effect was going to be 9, then the observed mean KOOS in one arm would have been x , and in the other arm it would have been $x+9$. If there is 20% cross-over in one direction, and you analyse by intention-to-treat, then the observed mean KOOS in one arm is now still x , and in the other arm it is now $[0.8(x+9) + 0.2x] = x+7.2$. We have assumed the standard deviation for the KOOS will be 15 (13,41,42,43,44,45). To account for and adjusting for baseline KOOS, we have assumed a correlation between baseline and follow up measurement of 0.25. This reduces the standard deviation to 13. $\text{Variance}_2 = (1-\rho^2) \text{variance}_1$ where $\text{variance}_1 = 15^2$, and $\rho = 0.5$ (From pg54 Julious, Sample sizes for clinical trials). Therefore new $\text{SD} = \sqrt{168.75} \approx 13$. The intracluster correlation coefficient of the KOOS amongst surgeons is likely to be around 0.056 (60). Using this value, and assuming there will be approximately 5 patients per surgeon, gives a design effect of 1.224. [design effect = $1 + (0.056 * (5-1)) = 1.224$]. We have adjusted for clustering among surgeons through multiplying by the square root of the design effect (1.106) to obtain a standard deviation in the surgical arm of 14.4. In the non-surgical intervention arm of the trial, the number and variety of physiotherapists treating each patient is variable, and clustering by physiotherapist is not appropriate.

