However, the components of the non-surgical intervention are likely to be similar with each centre, and vary between centres, so clustering on centre within the non-surgical intervention arm is more appropriate. We have assumed that the intracluster correlation coefficient of the KOOS in the non-surgical intervention arm of each centre is 0.056. If there are 10 patients per centre, we get a design effect of 1.504. [design effect = $1+(0.056*(10-1)) = 1.504$]. We have adjusted for clustering in the physiotherapy arm through multiplying by the square root of the design effect (1.226) to obtain a standard deviation in the physiotherapy arm of 15.9. Using 90% power, 2-sided $p=0.05$, with a difference of 7.2, and standard deviations of 14.4 and 15.9, this gives a sample size of 95 per group. Allowing for 15% loss to follow up gives 112 per group.

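### Table 1 has two faulty rows: exactly 5 pilot sites falls in no band, and the crossover row sets a 24-month allowance against at most 9 months of follow-up

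*Protocol*

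**What the plan says.** Section 3 of the protocol sets up the pilot: "The study design incorporates a 9-month internal pilot". The DMC, the TSC and the funder review it to decide on progression. The same section says "We plan to open at least 5 sites during the pilot phase". Table 1 then gives these bands:

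- **Sites opened:** red 2 or fewer, amber 3-4, green more than 5.
- **Crossover rate:** red above 50%, amber 20-50%, green below 20%.
- **Off-protocol intervention rate:** red above 30%, amber 10-30%, green below 10%.

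Table 1 does not say over what follow-up, in which direction or in which arm crossover is counted. It gives no action for amber.

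Section 9.1 uses the same 20% for the 24-month primary outcome: "To account for 20% unidirectional crossover from the non-surgical arm to the surgical arm, we have used an MCID of 7.2".

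Three other places bear on what a 9-month pilot can show. Section 1.2.2 has PKT delivered "over a period not exceeding 4 months". Section 6 says of the fidelity form that the "proforma will be completed for each participant approximately 6 months post intervention", and notes that waiting lists can lengthen the time since randomisation. Section 2.2 records further operations on the study knee at 12 and 24 months.

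**The concern.** The site row gives no classification when the site plan is met exactly at its minimum.

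The crossover row takes a cumulative 24-month allowance and uses it as a limit on a proportion seen in patients with 0 to 9 months of follow-up. Crossovers still to come are counted as none, so the error runs in one direction, towards green. A programme of up to 4 months followed by a surgical waiting list makes late crossover plausible.

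The off-protocol row has a related difficulty. A fidelity form at its nominal time can fall 4 + 6 = 10 months after PKT starts, which is outside the pilot.

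What is at stake is the progression decision. Crossover dilutes the intention-to-treat difference directly, and Section 9.2 plans no formal interim analysis. The committees could therefore read a reassuring figure from the pilot while the 24-month rate is heading beyond what the sample size allows for.

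**Working it through.** **Inputs.** Undiluted difference 9 ("so we have used a value of 9, the mid-point of this range"). Dilution rule "0.8(x+9) + 0.2x] = x+7.2", that is, difference = 9(1 − c) for crossover c. SDs 14.4 and 15.9, two-sided 5%, 90% power, 95 analysed and 112 recruited per group (all Section 9.1). Pilot 9 months and follow-up 24 months (Section 3).

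**1. The protocol's own sample size.** Combined SD = √[(14.4² + 15.9²)/2] = √230.085 = 15.17. For a difference of 7.2 at 90% power, the normal approximation gives 94 per group and the t distribution gives 95 (power 0.8993 at 94, 0.9023 at 95). Then 95/0.85 = 111.8, so 112. The stated figures reproduce.

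**2. Power at the crossover limits.** Standard error with 95 per group = 15.17 × √(2/95) = 2.20. Noncentral t, 188 degrees of freedom:

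| 24-month crossover | Difference | Difference/SE | Power |
|---|---|---|---|
| 20% | 7.20 | 3.27 | 90% |
| 31% | 6.21 | 2.82 | 80% |
| 40% | 5.40 | 2.45 | 68% |
| 50% | 4.50 | 2.04 | 53% |

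At 50% crossover, power is about 56% with 10% missing (112 × 0.9 ≈ 101 per group) and 60% with no loss (112 per group).

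**3. What the pilot would show.** The protocol gives no crossover timing, so assume even accrual over 9 months and a constant hazard h = −ln(1 − c)/24. The expected proportion crossed over at month 9 is 1 − (1 − e^(−9h))/(9h).

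- c = 20%: h = 0.0093, 9h = 0.084, observed proportion 4.1%.
- c = 50%: h = 0.0289, 9h = 0.260, observed proportion 11.9%.
- To show 20%, 9h must be 0.464, which is 71% at 24 months.
- To show 50%, the 24-month rate would be about 99%.
- If nobody crosses over in the first 4 months and the hazard is constant afterwards, c = 50% shows as about 4.5%.

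**4. Front-loaded switching.** Drop the 24-month constant hazard and keep even accrual with a steady rate inside the pilot. Showing 20% then needs 1 − e^(−0.464) = 37% of patients to have crossed over by their own month 9. For a true rate of 50% that is 0.37/0.50 = 74% of all crossovers. If switching were instead immediate after randomisation, 0.20/0.50 = 40% of crossovers would be enough. The more switching is concentrated at the start, the smaller the bias.

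**5. Precision.** With 20 recruits, about 10 are in the PKT arm. Two crossovers (20%) have an exact 95% confidence interval of 2.5% to 55.6%.

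**6. Sites.** The bands cover 0-2, 3-4 and 6 or more. The value 5 is missing.

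**The case against.** The strongest case on the other side has five parts.

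- **The other rows work.** Participants recruited and recruitment rate are untouched. A reader might infer that Table 1 as a whole cannot serve its purpose; the document does not support that. This stands.
- **The pilot percentages are assumed.** Even accrual and a constant hazard are not in the protocol. These are open-label patients already judged suitable for HTO, so early switching is plausible, and PKT data are recorded at each session. A reader might infer that the row will read green whatever the true rate. That goes too far: the pilot rate is an incomplete lower bound whose shortfall depends on timing. The direction of the error does not depend on the assumptions.
- **Amber is not a pass.** Green stops at the design assumption, so an observed 20-50% is flagged. This stands, but the rate first has to be observed.
- **The 50% line cannot be read two ways at once.** Read as a pilot proportion, it corresponds to about 99% at 24 months under the constant hazard; read as a 24-month rate, it corresponds to 53% power. This stands. The 53% holds only on the second reading.
- **There are mitigations, and definitions may sit elsewhere.** Section 9.2 plans a CACE analysis. Section 9.4 follows movement from the non-surgical to the surgical arm. Table 2 allows ±6 months on the fidelity form. Operational detail may be in a charter or analysis plan that is not shown. These soften the point, but none changes the printed limits, and leeway on a form's date does not create follow-up. No calculation shows that the off-protocol row would read green, so for that row the point is only who can be assessed.

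**Conclusion.** The point holds for two rows. The site row leaves out the plan's own minimum target, which is a plain drafting gap. The crossover row compares a proportion from at most 9 months with a 24-month allowance and so leans towards green.

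The size of the lean depends on timing. Under even accrual and constant hazard, 20% shows as about 4% and 50% as about 12%. With a steady rate within the pilot, a true 50% reaches the amber line only if about three-quarters of crossovers occur by month 9; fewer are needed if switching clusters right after randomisation.

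Read as a 24-month rate, amber runs from 90% down to about 53% power with 95 analysed per group, or about 56-60% at its lower end with less loss. This assumes one-way PKT-to-HTO crossover counted within the PKT arm, as in Section 9.1, and the SDs as printed. That section names a correlation of 0.25 but puts 0.5 into its formula; with 0.25 in the formula, power at 50% crossover would be about 45%.

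A reader might also infer that red must begin at 31%, where power reaches 80%. That would be a preference: the protocol sets no such floor.

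**What to change.** 1. Change the green site band to 5 or more.
2. Define the crossover row as PKT-to-HTO crossover in the PKT arm, and say whether the decision or the operation counts.
3. Compare with the bands a time-to-event estimate projected to 24 months, with its confidence interval and the assumptions behind the projection.
4. Print the power at each band limit (90% at 20%, 53% at 50%, with 95 analysed per group) so that the committees can judge an amber result.
5. Count off-protocol intervention only in patients with enough follow-up for it to be assessed.
6. Keep crossover, pooled over sites, under DMC/TSC review during recruitment.

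A second formal gate is not advised. Waiting for 40-50 PKT patients to reach 12 months means 80-100 randomised plus 12 months. With 224 recruited evenly over 24 months (9.3 a month), that falls at about months 21-23. With 20 recruited by month 9 and the other 204 evenly over the next 15 months (13.6 a month), it falls at about months 25-27. Either is too late for a stop/go decision.

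**Cost.** An amended table and a standing item for the committees. The downside is imprecision: an interval of about 3% to 56% from 2 of 10 patients cannot carry an automatic rule. For example, with a true rate of 20% and 10 PKT patients, 4 or more would cross over about 12% of the time. The projection should inform the decision and not trigger a stop by itself.
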